## BACKGROUND AND SIGNIFICANCE

Insulin resistance is a major contributor to the development of several obesity-related diseases. Despite the common link between obesity and insulin resistance, as many as one-third of obese adults appear to be "protected" against insulin resistance. Our preliminary findings indicate that insulin resistance can vary considerably even in a population of obese adults who are very similar in terms of the magnitude and distribution of their adiposity. **The overall goal of this project is to identify factors that "protect" some obese adults from becoming insulin resistant.** *Identifying mechanisms that help protect some obese adults from developing insulin resistance could lead to novel, targeted therapeutic and/or preventative strategies for obese adults who are insulin resistant.*

Excessive availability of fatty acids in the circulation (which are largely derived from subcutaneous adipose tissue) is one of the key factors underlying insulin resistance in obesity. Based on our preliminary findings, we contend that enhanced capacity for triglyceride storage in subcutaneous adipose tissue (thereby sequestering fatty acids - and attenuating their release) provides important protection against insulin resistance. This notion is not new, however, the specific metabolic events and/or cellular factors within subcutaneous adipose tissue that are responsible for more effective triglyceride storage are not known. *We hypothesize that obese adults who are protected against insulin resistance exhibit modifications in key factors that regulate adipose tissue structure and metabolic function (e.g., lipolytic regulation, adipogenic capacity (resulting in more, smaller fat cells), angiogenic capacity (enhancing capillarization), and fibrosis (altering extracellular matrix architecture))*

Although we contend that alterations in adipose tissue structure and metabolic function play a key role in determining insulin resistance in obesity, other factors obviously contribute as well. For example, because skeletal muscle is the predominant site of insulin-mediated glucose uptake, abnormalities in insulin signaling events within skeletal muscle also underlie systemic insulin resistance. Protein tyrosine phosphorylation (pTyr) plays critical role regulating key biological processes, including insulin signaling. Using state-of-the-art mass spectrometry-based proteomics, we can quantify hundreds of pTyr sites simultaneously, and by doing so we anticipate discovering novel pTyr targets that may differentiate insulin sensitive vs. insulin resistant obese adults. These findings will help identify new molecular mechanisms underlying insulin resistance, and will provide novel targets for preventing and treating type 2 diabetes and other obesity-related diseases.

In this project, we will measure insulin-mediated glucose uptake in a homogeneous cohort of abdominally obese adults, and then stratify them into three distinct groups based on their degree of insulin resistance. Our main comparisons will be made between the most- and least-insulin resistant groups.

**SPECIFIC AIM #1:** *Compare factors regulating triglyceride storage and adipogenesis in subcutaneous adipose tissue from insulin-sensitive obese adults compared with a well-matched cohort of insulin resistant subjects.*

**Hypothesis 1:** Compared with adipose tissue from obese adults who are insulin resistant, adipose tissue from those who remain relatively insulin sensitive will have: a) lower abundance and basal activity of lipolytic enzymes b) higher abundance and basal activity of esterification enzymes, c) greater anti-lipolytic response to insulin (measured *in vivo* and *in vitro*), d) greater expression of adipogenic markers (e.g., PPAR $\gamma$  and C/EBP $\alpha$ ), e) elevated adipogenic capacity (measured *in vitro*), f) higher adipocyte cell density (cells/cm $^2$ ), g) greater angiogenic capacity (measured *ex vivo*), and h) less adipose tissue fibrosis.

**SPECIFIC AIM #2:** *Identify other important and novel factors that contribute to the protection against insulin resistance in some obese adults.*

**Hypothesis 2A:** Targeted analyses in adipose tissue and skeletal muscle will reveal that specific markers of: a) macrophage infiltration, b) pro-inflammatory cytokine/adipokine abundance, and c) skeletal muscle lipid accumulation, as well as d) hepatic lipid accumulation, will be lower in obese adults who are relatively insulin sensitive compared with a well-matched cohort of insulin resistant subjects.

**Hypothesis 2B:** Unbiased proteomic analysis in skeletal muscle and adipose tissue will reveal novel differences between obese adults who are insulin sensitive compared with insulin resistant obese adults

## **RESEARCH DESIGN AND METHODS**

### **Overall strategy**

- We will recruit a cohort of abdominally obese adults who will be very similar in terms of body mass index (BMI), fat mass, fat free mass, waist circumference, and habitual physical activity behavior (sedentary).
- We will measure insulin sensitivity (hyperinsulinemic-euglycemic clamp) and then stratify the subjects into 3 groups based on their degree of insulin resistance. 1) "***Insulin resistant***" [**IR**], 2) "***Mildly insulin resistant***" [**MIR**], and 3) "***Non-insulin resistant***" [**NIR**]. The "cutoff points" used for stratifying our subjects into these 3 groups were defined by Stern et al., (25).
- We will also measure systemic fatty acid kinetics (stable-isotope dilution methods) and we will collect subcutaneous adipose tissue biopsy samples.
- In these adipose tissue samples, we will perform extensive, yet very relevant and integrated analyses of factors regulating fatty acid storage and mobilization, adipogenesis, fat cell size, capillarization, angiogenesis, and fibrosis.
- We will also collect skeletal muscle biopsy samples to assess factors in muscle that may also be different in insulin resistant [**IR**] and non-insulin resistant [**NIR**] obese adults.
- Several other important phenotypic measures will be performed to help characterize the subjects (e.g., subcutaneous and visceral adiposity [MRI analysis], hepatic lipid accumulation and degree of hepatic fibrosis [MRI analysis], basal metabolic rate, blood lipid profile)
- Our primary comparisons to assess factors contributing to protection against insulin resistance will be performed on the most-insulin resistant [**IR**] and least-insulin resistant [**NIR**] groups, but we will also perform correlational analyses using the entire subject population.

### **Subjects**

A total of 60 obese, pre-diabetic women [n=30] and men [n=30] will be recruited for this study. Eligible subjects will be homogeneous in terms of the magnitude and distribution of their adiposity (BMI: 30-40 kg/m^2; waist circumference: 88-98cm for women and 100-110cm for men), age (18-45 years old), and physical activity behavior (sedentary). All subjects must be weight stable ( $\pm 3$ kg for  $\geq 6$  months) and they will be screened with a detailed health history survey. Subjects will not be taking medications known to affect lipid or glucose metabolism. Anyone with evidence and/or history of cardiovascular or metabolic diseases will be excluded. All women will be pre-menopausal and will have regularly occurring menses. To avoid potential confounding hormonal effects, all women will be studied in the early follicular phase of their menstrual cycle.

Based on past experience, we anticipate that approximately 50% of the subjects who sign an informed consent document before undergoing our more involved screening procedures will not participate in this study (largely due to being deemed ineligible after screening or because of personal reasons). Therefore, we anticipate a total of 120 subjects will sign our informed consent document.

### **Inclusion Criteria**

- Body mass index [BMI]: 30-40 kg/m^2
- Age: 18-45 years
- All women must be pre-menopausal
- Non-exerciser: no regularly planned exercise/physical activity

### **Exclusion Criteria**

- Weight instability  $\geq \pm 3$ kg  $\geq 6$  months
- Medications known to affect lipid and/or glucose metabolism
- Pregnancy or actively breast feeding

[figure not shown]
### **Additional preliminary testing will be performed on subjects deemed eligible after initial screening visit**

- Physical activity questionnaire
- Urine pregnancy test for female subjects
- Body composition assessment (DEXA)

## Detailed clinical study procedures

Subjects will complete a physical activity questionnaire and a three day food journal before their hospital visit. On the morning of the study, subjects will be admitted to the Michigan Clinical Research Unit (MCRU) at 0700h. Subjects will arrive at the Michigan Clinical Research Unit (MCRU) in the University of Michigan Medical Center in the morning after an overnight fast. After arrival, subjects will rest quietly in their room for 30 min. We will then measure their resting metabolic rate (RMR) using a canopy-equipped metabolic cart (Vmax metabolic cart; Viysis, Inc.) for 20min. After RMR measurement, intravenous catheters (IVs) will then be placed in a forearm or hand vein of both arms. Approximately 1.5h after admission to the MCRU, we will begin primed, stable isotope infusions of [6,6 d2]glucose (to assess the rates of hepatic glucose production and systemic glucose uptake) and [d5]glycerol (to assess whole body lipolytic rate). At the same time we begin the tracer infusions, we will collect skeletal muscle (vastus lateralis) and subcutaneous abdominal adipose tissue biopsy samples. Approximately 2.5h after admission we will begin an infusion of [C]palmitate (to assess the rate of systemic fatty acid mobilization). Three blood samples will be collected in five minute intervals starting ~50min after beginning the [C]palmitate infusion. Immediately, after collection of these blood samples we will begin a hyperinsulinemic-euglycemic clamp (insulin infusion rate = 40 mU/m^2/min) to assess insulin resistance, as described previously by Defronzo, et al. (6). During the clamp procedure we will collect small blood samples every 5 minutes to assess blood glucose concentration and the glucose infusion rate will be adjusted as necessary to maintain euglycemia, as described previously (6). Thirty minutes after starting the hyperinsulinemic-euglycemic clamp procedure we will collect another skeletal muscle and adipose tissue biopsy samples to acquire a sample in the insulin stimulated condition. Finally, we will collect 5 blood samples during the final 20 minutes of the clamp. Detailed descriptions of these procedures can be found in our previous publications (8, 9, 16, 23), and blood sampling timeline is provided in Appendix 1 of this document.

We will also measure percent body fat using a Dual Energy X-ray Absorptiometry [DEXA: Lunar DPX, DEXA Scanner] and We also plan to measure hepatic fibrosis, the amount of fat stored in the liver, intra-abdominal adiposity (i.e., visceral adiposity), and visceral fat (or intra-abdominal fat) using magnetic resonance imager (MRI) with elastography – but depending on scheduling, these tests may be performed on a separate occasion.

The blood collection during the clinical trial will be conducted in the Michigan Clinical Research Unit (MCRU), which is located in room 1111 of the Cardiovascular Center (CVC). The clinical suite is a research unit, specifically designed for performing clinical procedures in human subjects. The suite contains a padded patient treatment table for blood draws, IV placements and biopsies. A television is mounted on the wall for participant's entertainment during the testing procedures.

The intravenous (IV) catheter placement and blood draws will be performed by [name], [name], or a qualified member of [name] research team. [name] research staff members, [name], [name], [name], and [name] have completed Phlebotomy training offered through MLearning (supervisor: [name], MSN, RN, CNS-BC, OCN), and they are trained and qualified to perform venipuncture blood draws.

[name] will provide clinical oversight/responsibility for this study. In general, [name] will not be present in the MCRU during the testing, but he will be alerted in advance to when all testing will be occurring, he will be available for immediate consultation by phone, and available to come to the MCRU within ~15 min to attend to any concerns that may need his direct attention. In the event [name] is unavailable/out of town during a testing day, arrangements will be made with either Drs. [name], [name], [name], or [name] to provide direct clinical oversight during that particular experiment.

## **SOP for Skeletal Muscle and Subcutaneous Adipose Biopsies**

### **Screening and pre-visit procedures**

- Anti-coagulant medication (e.g., Coumadin, Rivaroxaban) and Lidocaine allergy/sensitivity are exclusion criteria for the biopsy procedure.
- Aspirin (ASA) and/or other nonsteroidal anti-inflammatory medications (NSAIDS; e.g., Ibuprofen, Naproxen) must be avoided for 3 days before the biopsy procedure (Tylenol can be used)

Before performing the tissue biopsies, [name] (or his qualified co-investigator who is performing the biopsies) will:

- 1) confirm the participant's identification
- 2) thoroughly explain the biopsy procedures to the participant, describing what they may experience during the procedures.
- 3) confirm the location of the procedures (e.g., left or right thigh for muscle biopsy - and left or right of the umbilicus for the adipose tissue biopsy/aspiration

### **Skeletal Muscle Biopsy Procedure**

- Confirm that the participant does not have any known allergies/sensitivity to local anesthetic (e.g., Lidocaine/Bupivacaine) – this should also have been addressed before/during informed consent process.
- If necessary, shave ~5" x ~5" square above the vastus lateralis
- Put on surgical gown, mask and bonnet (assistants in procedure room also must wear mask and bonnet)
- Disinfect skin above the vastus lateralis with betadine
- Put on sterile gloves and all the following procedures must be performed using aseptic technique
- Create sterile field on tray top and around the betadine covered area of the participant's thigh
- Infiltrate skin and underlying tissue with 2% lidocaine using a 25g x 1.5" needle (~6-10 ml of lidocaine: total dose of lidocaine not to exceed 4.5mg/kg)
- Make an incision above the vastus lateralis with a #10 scalpel (cut skin and try to cut fascia if possible)
- Apply pressure to incision site with sterile gauze until bleeding stops (or is very light)
- While pressure is being applied to the thigh, the biopsy assistant attaches a 3-way stopcock to a 60cc syringe
- One end of sterile pressure tubing is attached to the sterilized biopsy needle (4-5g Bergstrom or UCH biopsy needle), and the other end of the tubing is handed to the assistant to attach to their 3-way stopcock/60cc syringe set-up for suction.
- The biopsy needle is inserted into the incision with firm pressure. The biopsy needle is inserted past the fascia, in the location/direction of the applied anesthetic
- Once the biopsy needle is fully inserted, the biopsy assistant pulls back firmly on the plunger of the 60cc syringe to apply steady suction. The sample is collected by closure of the biopsy needle – To increase sample yield, the biopsy needle can be quickly rotated then opened and closed 3-5 times to obtain a few “snips” of sample before removing the biopsy needle from the thigh.
- The sample is placed on a sterile absorbent pad, and pressure is applied to the biopsy site with sterile gauze
- The biopsy assistant quickly rinses/cleans the sample with saline and gently dabs the sample on the absorbent pad to remove excess liquid. The sample is placed in collection vial - and placed in liquid N2.
- While assistant is cleaning and storing the sample, manual pressure is applied to the incision site
- The biopsy procedure can be repeated in the same incision site (or separate preprepared site) if more tissue is needed.
- When the entire biopsy procedure is finished, firm direct pressure is applied to the incision site until bleeding stops (~10 minutes)
- Incision site is cleaned with 70% ethanol and dried with sterile gauze
- The incision is closed with steri-strips and an overlaying Tegaderm bandage (with absorbent pad)
- A pressure dressing is applied to the thigh until bedtime the night of the biopsy procedure
- Participant is instructed to avoid water submersion for 2 days and to keep the bandages on for 5 days.
- Upon discharge, provide participant with pre-printed post-procedure care instructions with emergency contact information.

### **Subcutaneous Adipose Biopsy Procedure**

- Confirm that the participant does not have any known allergies/sensitivity to local anesthetic (e.g., Lidocaine/Bupivacaine) – this should also have been addressed before/during informed consent process.

- Clean the anterior abdominal wall in the periumbilical area with betadine
- Put on sterile gloves and all the following procedures must be performed using aseptic technique
- Create sterile field on tray top and around the betadine covered area of the participant's abdomen
- The location of the incision will be 5-10cm lateral to the umbilicus – infiltrate the skin and underlying tissue in this location with ~1-2ml of 2% lidocaine using a 25g x 1.5" needle. Then, with the lidocaine needle inserted at the intended incision site direct the needle at ~20 degree angle with the abdomen and anesthetize a quadrant of the abdomen with a 1.5" radius between the intended incision site and the umbilicus (this will anesthetize the sampling region). Total lidocaine dose for abdomen = 5-8ml of 2% lidocaine; total dose of lidocaine must not exceed 4.5mg/kg – this includes any lidocaine administered for any other procedures during the test day).
- Make an incision in this anesthetized site (5-10cm lateral to the umbilicus) with #10 or #11 scalpel
- Apply pressure to incision site with sterile gauze until bleeding stops (or very light)
- While pressure is being applied to the abdomen, the biopsy assistant attaches a 3- way stopcock to a 60cc syringe
- One end of sterile pressure tubing is attached to the sterilized biopsy needle (4-5g Bergstrom or UCH biopsy needle), and the other end of the tubing is handed to the assistant to attach to their 3-way stopcock/60cc syringe set-up for suction.
- For collection of the core tissue sample, insert the biopsy needle (4-5g Bergstrom or UCH biopsy needle) into the incision, directed at ~20 degree angle with abdomen. The biopsy needle is inserted ~2cm in the direction of the anesthetized area (toward the umbilicus).
- Once the biopsy needle is inserted ~2cm, suction is applied to the needle (by an assistant) via an attached extension tubing and 60cc syringe. The sample is collected by closure of the biopsy needle – and extracted.
- The sample is placed on a sterile absorbent pad. The biopsy assistant rinses and cleans the sample with saline and gently dabs the sample on a on absorbent pad to remove excess liquid
- The sample is placed in collection vial (typically containing formalin).
- The biopsy procedure can be repeated in the same incision site if a larger core sample is needed.
- After completing the core sample collection, more tissue can extracted using aspiration.
- For the subcutaneous adipose tissue aspiration method, attach a sterilized aspiration needle (e.g., Spirotri cannula) to sterile pressure tubing, attached to sterile 60cc syringe with stopcock attached.
- Insert aspiration needle into incision site (~3cm), retract plunger, and apply constant negative pressure with the syringe during the aspiration process.
- With needle inserted into this incision site, one hand lightly pinches the surface of the biopsy site, while the other hand gentle maneuvers the biopsy needle under the skin for 30-60 seconds to extract tissue (tissue will accumulate in the syringe)
- Remove aspiration needle from incision site –
- The extracted tissue can be removed from the syringe either by ejecting through the tip of the syringe – or by removing the syringe plunger and pouring the tissue out. In both cases the tissue should be placed on a sterile absorbent pad for the biopsy assistant to clean and process the sample.
- Aspiration procedure can then be repeated in the same incision, but try to direct the needle in a slightly different "track" within the anesthetized area in order to avoid tissue collection within exactly the same area.
- After completion of all tissue extraction, pressure should be applied to the biopsy site for 5-10 min. • Clean biopsy site with alcohol, place steri-strip on site to close the small incision, and tegaderm bandage is then placed over the steri-strips.
- Apply ice to biopsy site for 10-20 min
- Participant is instructed to keep the bandages on for 5 days.
- Upon discharge, provide participant with pre-printed post-procedure care instructions with emergency contact information.

As an alternative approach, a 1.5in x 16g needle or a "Coleman needle" may be used for tissue aspiration instead of the Spirotri cannula, under the same conditions as described above. However, when using these alternative needles, more aspiration "passes" may be required to extract the necessary amount of adipose tissue.

**Diets for clinical study:** Subjects will be advised what they should be eating in the 3 days leading up to their hospital visit to maintain energy balance (total daily energy intake will be approximated to be  $370 + (21.6 \times \text{fat free mass}) \times 1.5$ ), with a macronutrient content of approximately 55% carbohydrate, 30% fat, and 15% protein, which represents the macronutrient content of a “typical” western diet (2). On the experimental day, subjects will arrive in the overnight fasted state and will not eat anything until completion of the clamp procedure.

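### Do two biopsy sessions on one day break the SOP's own lidocaine limit?

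*Combined protocol and SAP*

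**What the plan says.** The section on detailed clinical study procedures sets two sampling times on the same day. The first comes about 1.5 h after the 07:00 admission: "At the same time we begin the tracer infusions, we will collect skeletal muscle (vastus lateralis) and subcutaneous abdominal adipose tissue biopsy samples". The second comes 30 minutes into the clamp: "we will collect another skeletal muscle and adipose tissue biopsy samples to acquire a sample in the insulin stimulated condition". Appendix 1 starts the clamp at 10:30, so the sessions fall at about 08:30 and 11:00.

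The Skeletal Muscle Biopsy Procedure uses 2% lidocaine and gives an approximate volume with a limit: "6-10 ml of lidocaine: total dose of lidocaine not to exceed 4.5mg/kg". The Subcutaneous Adipose Biopsy Procedure gives "Total lidocaine dose for abdomen = 5-8ml of 2% lidocaine". It sets the same 4.5 mg/kg limit in mandatory terms and defines its scope: "this includes any lidocaine administered for any other procedures during the test day".

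Both SOP sections allow repeat sampling. For muscle: "The biopsy procedure can be repeated in the same incision site (or separate preprepared site) if more tissue is needed". For fat: "The biopsy procedure can be repeated in the same incision site if a larger core sample is needed". Neither mentions the scheduled second session, and neither gives a lidocaine volume for a repeat. Weight enters eligibility only through "Body mass index [BMI]: 30-40" kg/m² and weight stability. No body-weight bound is stated.

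**The concern.** Infiltration with lidocaine is a step in both SOP procedures, and each procedure is carried out twice on the day. A reader who applies the stated volumes each time obtains a total that the SOP's own limit does not allow for many body sizes within the BMI range. On that reading the schedule, the volumes and the limit cannot all be met.

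Two things would be at stake. One is participant safety, if the volumes were followed and the limit overlooked. The other is the insulin-stimulated samples, because any shortage of permitted anaesthetic would fall on the second session. The muscle section also states the limit without saying that it covers the whole test day, so the two sections look inconsistent.

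**Working it through.** The documents state no total in mg and no weight threshold, so there is no derived figure of theirs to reproduce. The check is direct arithmetic.

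**Inputs**
- Thigh: about 6-10 ml of 2% lidocaine (Skeletal Muscle Biopsy Procedure).
- Abdomen: 5-8 ml of 2% lidocaine (Subcutaneous Adipose Biopsy Procedure).
- Limit: 4.5 mg/kg over the test day (same section).
- BMI: 30-40 kg/m² (Inclusion Criteria).
- Conversion: 2% = 20 mg/ml. This is a unit conversion and is not written in the documents.

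**Formulas**
- Total (mg) = total volume (ml) x 20.
- Weight below which the total exceeds the limit (kg) = total / 4.5.
- Equivalent height (m) = square root of (weight / BMI).

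**Lowest stated volumes, under each way the volumes could apply**

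| How the volumes apply | Volume (ml) | Total (mg) | Weight (kg) | Height at BMI 30 / 35 / 40 (m) |
|---|---|---|---|---|
| Both tissues at both sessions | (6 + 5) x 2 = 22 | 440 | 97.8 | 1.80 / 1.67 / 1.56 |
| Thigh twice, abdomen once | 6 x 2 + 5 = 17 | 340 | 75.6 | 1.59 / 1.47 / 1.37 |
| Thigh once, abdomen twice | 6 + 5 x 2 = 16 | 320 | 71.1 | 1.54 / 1.43 / 1.33 |
| Each once for the day | 6 + 5 = 11 | 220 | 48.9 | 1.28 / 1.18 / 1.11 |

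The threshold runs from 48.9 to 97.8 kg, a factor of two, depending only on a reading that the text does not settle. On the last row practically no eligible adult is affected.

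**Highest stated volumes.** Both tissues twice gives (10 + 8) x 2 = 36 ml = 720 mg, or 160 kg. Each once gives 18 ml = 360 mg, or 80 kg. These weights do not mark a contradiction. A range is satisfied by any value inside it, so volumes and limit are incompatible only where the lowest volumes already exceed the limit.

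**Two examples (heights assumed)**
- 1.65 m at BMI 30: 30 x 1.65² = 81.7 kg, and the limit is 81.7 x 4.5 = about 367.5 mg (18.4 ml). One set at the lowest volumes uses 220 mg and leaves 147.5 mg, or 7.4 ml. A full second set at the lowest volumes would be 11 ml and does not fit. Repeating only the thigh (6 ml) or only the abdomen (5 ml) does fit.
- 1.75 m at BMI 35: 35 x 1.75² = 107.2 kg, and the limit is 482 mg (24.1 ml). The lowest volumes fit on every row, since the largest is 22 ml.

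**The two statements of the limit.** Both sections give 4.5 mg/kg. The adipose section extends it to every other procedure on the test day, which necessarily includes the muscle biopsy. The shorter wording is less explicit but does not contradict the longer one.

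**The case for a change.** The strongest case for acting is that reading the volumes as given once is not established either. The lines on repeat sampling are written for obtaining more tissue or a larger core, not for a planned session about 2.5 h later. The muscle section also allows a separate site and is silent on lidocaine for it. The stated total for the abdomen may be only the sum of the two infiltration steps described beside it at one sitting. An operator working from the muscle section alone would not see the test-day scope. The cost of clarifying is a few words.

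Most of this stands as description. The SOP does not say how its volumes apply at the second session, and if both full volumes are repeated, the lowest of them do not fit below 97.8 kg.

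What does not stand is the step from there to a fault. The adipose section's limit anticipates several infiltrations in a day and ranks above the volumes, one of which is only approximate. No excess dose is authorised on any reading. Loss of the second samples is inferred from the least favourable reading; nothing in the documents shows it. The documents give no heights or weights, so the share of participants below any of these thresholds cannot be computed.

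**Conclusion.** The concern does not call for a change to the plan. It identifies a missing detail: whether the lidocaine volumes are per session or per test day. The weight below which the lowest volumes would exceed the limit is 97.8 kg if both tissues are fully re-infiltrated, 75.6 or 71.1 kg if only one is, and 48.9 kg if neither is. All four figures are nominal, because they rest on 20 mg/ml for 2% and on an approximate thigh volume. The conflict exists only on readings that the text does not establish, and the binding test-day limit keeps an operator who follows the SOP within it on all of them.

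How the schedule, the volumes and the limit are worded together across the three sections is for the responsible clinicians to reconcile. That would write down existing practice. No view is taken here on which reading is right. No stated figure is shown to be wrong, and neither the statistical analysis nor the sample size calculations use these volumes.
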